Primary results available																														
Present data																														
Publish main results																														
Grant completed																														

Appendix 3: Steno Hypoglycaemia Questionnaire

HYPOGLYCAEMIA

Minor events no. of events
(since last contact)

Major events (without coma)* no. of events BG: mmol/l
(since last contact) (average)

- Potential cause:

Too little food	Physical activity	Alcohol	Betablocker	Insulin	Unknown
 1	 2	 3	 4	 5	 6

- Treatment:

Carbohydrate	Glucagon	Glucose iv	Other
 1	 2	 3	 4

Major events (with coma)* no. of events BG: mmol/l
(since last contact) (average)

- Potential cause:

Too little food	Physical activity	Alcohol	Betablocker	Insulin	Unknown
 1	 2	 3	 4	 5	 6

- Treatment:

Carbohydrate	Glucagon	Glucose iv	Other
 1	 2	 3	 4

* Coma is defined as unconsciousness during a hypoglycaemic event.
Major event is one requiring assistance for recovery

Appendix 4: Contraception

For women of childbearing potential in REMOVAL, acceptable forms of effective contraception include:*

1. Established use of oral, injected or implanted hormonal methods of contraception (note oestrogens may decrease glucose-lowering effect of oral glucose-lowering medications including metformin)
2. Placement of an intrauterine device (IUD) or intrauterine system (IUS).
[Consideration should be given to the type of device or system being used, as there are higher failure rates quoted for certain types, e.g. steel or copper wire]
3. Barrier methods of contraception: Condom or Occlusive cap (diaphragm or cervical/vault caps) – must be combined with spermicidal foam/gel/film/cream/suppository.
4. Sole male partner has been sterilised with appropriate post-vasectomy documentation of the absence of sperm in ejaculate.
5. True abstinence: When this is in line with the preferred and usual lifestyle of the subject. Periodic abstinence (e.g., calendar, ovulation, post-ovulation methods) and withdrawal are not acceptable methods of contraception.

*See MHRA “Clarification of contraceptive wording in clinical trials conducted in the UK - Version 2 amended 21st May 2010”

Appendix 5: Microalbuminuria definitions

For the presence or absence of microalbuminuria to be judged in relation to the inclusion criteria, the results of local assays conducted on at least two separate urine specimens must be available. The final decision will lie with the site Principal Investigator according to local protocols, guided by the following criteria.

Units	Definition	
	Male	Female
First morning sample		
mg/ mmol ¹	≥ 2.5	≥ 3.5
mg/g ¹	≥ 25	≥ 35
µg/ mg ¹	≥ 25	≥ 35
mg/L*	≥30	
Timed		
µg/ min	>20	
mg/ 24 hours	>30	
¹ ACR = albumin: creatinine ratio; * simple concentration (not preferred method)		

Occurrence of new microalbuminuria during the trial will be judged according to local assays, the results of which will be recorded in the eCRF.

Central assays may later be performed on stored urine aliquots to support the microalbuminuria secondary endpoint analysis.

Appendix 6: Abbreviated follow up (final 50 participants)

Calendar month randomized	Number of participants affected	Visit window adjustment	Abbreviation of follow-up (months)
Up to end March 2014	(379)	Visit 15 – Visit 16 window 3 months (per protocol)	0 (per protocol)
April 2014	8	Visit 15 – Visit 16 window reduced to 2 months	1
May 2014	8	Visit 15 – Visit 16 window reduced to 1 months	2
June 2014	12	Visit 15 omitted (i.e. Visit 14 – Visit 16 window reduced to 3 months)	3
July 2014	7	Visit 14 – Visit 16 window reduced to 2 months	4
August 2014	6	Visit 14 – Visit 16 window reduced to 1 month	5
September 2014	7	Visit 14 and 15 omitted (i.e. Visit 13 – Visit 16 window reduced to 3 months)	6
October 2014	1	Visit 13 – Visit 16 window reduced to 2 months	7
November 2014	1	Visit 13 – Visit 16 window reduced to 1 month	8
	50		

Please refer to Schedule of Assessments (page 10) for visit windows “per protocol”
 
These arrangements affect a total of 50 participants at the following sites (site number):
 
Canada: Ottawa (12)
 
Australia: Royal Melbourne (16), Prince Alfred, Sydney (17)
 
Denmark: Steno Diabetes Center (13)
 
Netherlands: Maastricht (14)
 
UK: Aberdeen (21), Aintree (7), Ayr (24), Royal Infirmary Edinburgh (19), Hull (6), London(UK)(8)

1. INTRODUCTION

1.1. STUDY BACKGROUND

Intensive glucose control reduces long term rates of cardiovascular disease (CVD) in people with type 1 diabetes (T1DM) but the majority of individuals affected by the condition do not currently achieve glucose targets with standard insulin therapy. Upward insulin dose titration may lead to weight gain, hypoglycaemia and dyslipidaemia. Metformin has the potential for addressing these issues as it may (i) reduce insulin dose for a given achieved HbA1c; (ii) promote weight stabilization; (iii) be associated with low rates of hypoglycaemia; and (iv) reduce LDL cholesterol – even on a background of statin therapy. It may also have direct and potentially beneficial cardiovascular effects.

Common carotid artery intima-media thickness (cIMT) is increased in type 1 diabetes. cIMT reliably predicted cardiovascular events in DCCT and has been successfully targeted by metformin in a number of small studies in conditions other than type 1 diabetes.

1.2. STUDY OBJECTIVES

The primary objective of the study is to assess whether three years treatment with metformin 1000mg bd added to titrated insulin therapy (towards target HbA1c 7.0% / 53 mmol/mol) reduces atherosclerosis, as measured by progression of cIMT, in adults with confirmed type 1 diabetes aged 40 years and over and at increased risk for CVD.

Secondary and tertiary objectives are to examine over the same period the effect of metformin on other markers of diabetic micro- and macrovascular complications and intermediate disease-related biomarkers.

1.3. STUDY DESIGN

The study is a randomised, double-blind, placebo controlled trial. Subjects will be randomised to either oral metformin or matching placebo. After recruitment each subject will remain in the study for three years during which they will be followed up by telephone and during clinics (telephone follow-up at weeks 1 and 2 and months 15, 21, 27 and 33 and clinic visits at months 3, 4, 6, 9, 12, 18, 24, 30 and 36). The primary outcome will be measured at baseline and at months 12, 24 and 36.

1.4. SAMPLE SIZE AND POWER

Assuming a mean linear progression of 0.044mm over three years (in the control arm) and a standard deviation (SD) for progression of 0.05mm and to have 90% power at a 5% significance level to detect a difference of at least one third of a SD (0.0167 MM) in three year progression of averaged mean far wall cIMT between treatment arms we will require 200 subjects per treatment group. Allowing for 20-25% drop-outs/discontinuations, 500 subjects, in total, will be recruited.

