Rationale:	
Intensive glucose control reduces long term rates of cardiovascular disease (CVD) in people type 1 diabetes (T1DM) but the majority of individuals affected by the condition do not currently achieve glucose targets with standard insulin therapy. Upward insulin dose titration may lead to weight gain, hypoglycaemia and dyslipidaemia. Metformin has potential for addressing these issues as it may: (i) reduce insulin dose for a given achieved HbA1c; (ii) promote weight stabilization; (iii) be associated with low rates of hypoglycaemia; and (iv) reduce LDL cholesterol - even on a background of statin therapy. It may also have direct and potentially beneficial cardiovascular effects.
 
Progression of carotid artery intima-media thickness (cIMT) is the primary endpoint as this is accelerated in type 1 diabetes. cIMT reliably predicted cardiovascular events in DCCT and has been successfully targeted by metformin in a number of small studies in conditions other than type 1 diabetes. The secondary endpoint is a composite of clinically-relevant markers of microvascular and macrovascular prognosis.

Product, Dose, Modes of Administration:	
Single-blind placebo Run-In: One tablet once daily with the evening meal.
 
Double-blind treatment period: Oral metformin (as Glucophage 500 mg x 2 twice daily) titrated from initial 500 mg to target 2000 mg daily/ matching placebo.

Sample Size:	500 enrolled participants.
Randomisation:	By telephone call to the study Interactive Voice Response System (IVRS) or electronically via the portal providing the study electronic Case Report Form (as provided by the Robertson Centre for Biostatistics, University of Glasgow).

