** N.B. All Visit 1 assessments [including carotid IMT, retinal imaging and ENDOPAT] MUST be completed within 4 weeks PRIOR TO randomization**

¹ VISIT 14 and VISIT 15 time windows altered or omitted for participants randomized after the end of March 2014 – see Appendix 6 ² VISIT 17 must be at least one week after Visit 16

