Other assessments: Serum C-peptide will be measured in local laboratories at the screening visit: participants will be withdrawn before randomisation in cases where this is > 200 pmol/L (= 0.2 nmol/L or 0.6 ng/ml). Although the risk of lactic acidosis is almost negligible,⁴⁸ plasma lactate will be monitored according to the Schedule of Assessment in local laboratories; participants with values > 3.0 mmol/L (>27 mg/dL) will be recalled for clinical assessment within one week and treatment discontinued if this level is sustained: where possible, blood samples for lactate will be performed without a tourniquet ("uncuffed") and following minimal exertion (this approach will be adopted for all repeat lactate measurements). Full blood count and serum vitamin B12 (cobalamin) concentrations will also be monitored during the study in view of the small risk of metformin induced B12 deficiency identified in recent papers by the applicants (CS/ SL): concentrations fell by 80 pmol/L with prolonged therapy, although rarely outwith the reference range (150-550 pmol/L).^{18,49} Any individuals whose levels do fall below the reference range (<150 pmol/L) and who do not wish to discontinue therapy will be referred to their primary care physician for consideration of replacement therapy.

Long-term follow-up: The primary and secondary outcomes of the study are robust, but they are surrogates for long-term CVD risk. Where national competent authorities permit, we will seek informed consent from all participants to "flag" them in national systems using national health numbers to permit outcome assessment and to receive notifications of deaths. This will be led by applicant IF who has particular expertise in this area.

c) Sample handling storage and shipping

Following pre-processing and aliquoting, blood and urine samples will be stored locally at -70°C or -80°C according to the study Sample Handling Plan prior to shipping to the central laboratory in Glasgow (Applicant NS). All study samples will be sent on dry ice using contracted couriers at annual intervals. All samples will be stored on arrival at -80°C .

d) Statistical considerations/ number of subjects to be included in the study

Primary endpoint cIMT: For the primary endpoint of cIMT there will be a baseline measurement and repeat measurements at year 1, 2 and 3 (visits 8, 12 and 16). All those with a baseline and at least one follow up measurement will be included in analysis.

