We intend to analyse IMT data using repeated measures regression analysis assuming a linear progression in IMT measurements. We expect a mean progression of 0.044mm over 3 years (in the control arm) and a standard deviation (SD) for progression of 0.05 mm; therefore a final sample size of 200 per treatment arm will provide 90% power (at 5% significance level) to detect a difference of at least one third of an SD (0.0167mm) in 3 year progression of averaged mean cIMT between treatment arms - an effect size more conservative than reported for acarbose, statins, and TZDs on cIMT.

We therefore aim to recruit 500 patients (allowing for around 20-25% treatment discontinuation/ drop-out) and making the very conservative assumption that all those discontinuing treatment/ and withdrawing consent would not even have one follow up measurement (in reality this may occur after one or more follow up cIMT measurements so power will be more than this estimate).

Rates of progression and variation of common carotid artery IMT vary widely between different studies and data from T1DM patients, other than the patients in DCCT/EDIC who are younger than this trial participants, are sparse. Our estimate of progression rate over three years (0.044 mm) is at the lower boundary of that reported by Bots in a meta-analysis of cIMT progression rates of control groups (almost all non-diabetic) from published RCTs.⁵⁰ In that analysis the annual rate of change in mean cIMT was 0.0176 mm (95% CI, 0.0149 to 0.0203). Whilst many of the control group participants in this pooled analysis were not on statins (in contrast to many REMOVAL participants with T1DM) almost all were non-diabetic so that their progression rate would be expected to be lower than in diabetes.

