1.6.3. CURRENT PROTOCOL

The current version of the protocol at the time of writing is version 3.0, dated 9th November 2015 and the accompanying NHS GG&C R&D protocol filenote. Future amendments to the protocol will be reviewed for their impact on this SAP, which will be updated only if necessary. If no changes are required to this SAP following future amendments to the protocol, this will be documented as part of the Robertson Centre Change Impact Assessment processes.

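### SAP 1.4 gives 90% power on 500 recruited, but Protocol Appendix 6 implies 429 randomised; label 500 as the design basis and state power for 429.

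*SAP*

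**What the plan says.** SAP 1.4 assumes an SD of 0.05 mm for three-year progression and a target difference of one third of an SD (0.0167 mm). It asks for 200 per group for 90% power at the 5% level, and continues: "Allowing for 20-25% drop-outs/discontinuations, 500 subjects, in total, will be recruited".

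The Protocol carries the same 500 in three places:
- Section 1 (Synopsis): "500 enrolled participants".
- Section 6 d): "We therefore aim to recruit 500 patients". The loss allowance is described there as "making the very conservative assumption" that nobody who stops treatment or withdraws has even one follow-up scan.
- Section 15: 500 is given as the number that needs to be recruited.

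Protocol Appendix 6 is headed "Abbreviated follow up (final 50 participants" and is arranged by calendar month of randomisation. It shows 379 in brackets up to the end of March 2014, then 8, 8, 12, 7, 6, 7, 1 and 1 for April to November 2014. The footnote to the Schedule of Assessments marks the same cut-off: "VISIT 14 and VISIT 15 time windows altered or omitted for participants randomized after the end of March 2014".

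SAP 1.6.3 dates the SAP: "The current version of the protocol at the time of writing is version 3.0, dated 9th November 2015".

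**The concern.** The SAP states, in the future tense and without a label, a trial size that the Protocol's own appendix indicates was not reached. Recruitment had ended by the time the SAP was written. Nothing else in the SAP corrects this: section 1.6.4 (deviations) mentions only biomarker assays, and the version history in section 3 lists only subgroups and the wording of the primary model.

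What is at stake is how the result is read. Someone weighing a neutral primary result would take from SAP 1.4 that the trial had 90% power even after losing 20-25% of its participants. That figure belongs to a trial of 500.

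**Working it through.** **Inputs.** From SAP 1.4: SD 0.05 mm, difference one third of an SD (0.0167 mm), 5% level, 90% power, 200 per arm, loss 20-25%. From Protocol Appendix 6: the monthly counts. Assumed, because not stated: a two-sided test and equal arms. Two-sided is the variant that fits, since a one-sided 5% test would need only 154 per arm.

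**Step 1. Reproduce the plan.** Two-sample normal calculation, with Φ the standard normal distribution function:
- n per arm for 90% power = 2 × ((1.960 + 1.282)/(1/3))² = 189.1, so 200 is a rounded-up figure.
- Power at 200 per arm = Φ((1/3)/√(2/200) − 1.960) = Φ(3.333 − 1.960) = 91.5%.
- Inflation: 400/(1 − 0.20) = 500. At 25% loss, 500 leaves 375 evaluable (187.5 per arm), with power 89.8%.

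The plan's figures therefore hold for 500 at both ends of its allowance, to within rounding.

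**Step 2. Number randomised.**
- April to November 2014: 8 + 8 + 12 + 7 + 6 + 7 + 1 + 1 = 50.
- Total: 379 + 50 = 429.
- Shortfall: 500 − 429 = 71, and 71/500 = 14.2%.

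**Step 3. Same calculation at 429.** Power = Φ((1/3)/√(2/n) − 1.960). The difference detectable with 90% power = 3.2415 × √(2/n) × 0.05 mm.

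| No usable follow-up | n per arm | Power | 90%-power difference |
|---|---|---|---|
| 0% | 214.5 | 93.2% | 0.0157 mm |
| 10% | 193.1 | 90.6% | 0.0165 mm |
| 20% | 171.6 | 87.0% | 0.0175 mm |
| 25% | 160.9 | 84.8% | 0.0181 mm |

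Noncentral t gives 93.1%, 90.4%, 86.8% and 84.6%. Using the rounded 0.0167 mm in place of exactly one third of an SD raises the normal figures by about 0.1 point.

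**Step 4. Loss that 429 can absorb at 90% power.** The total needed is 2 × 189.1 = 378.3, and 1 − 378.3/429 = 11.8% (50 people). With 190 per arm it is 49 people (11.4%). With the 191 per arm required by noncentral t it is 47 people (11.0%).

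**Step 5. Shortened follow-up, not included above.** Appendix 6 removes 8×1 + 8×2 + 12×3 + 7×4 + 6×5 + 7×6 + 1×7 + 1×8 = 175 participant-months. The planned total is 429 × 36 = 15,444, so the loss is 1.1%.

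**The case against.** **A SAP may restate the design calculation.** SAP sections 1.1 to 1.5 are background in design-stage language, and no analysis or decision rule uses the 500. SAP 2.2 will report the numbers randomised and withdrawn, and SAP 2.4.1 the 95% confidence interval, which is the proper basis for interpretation. All of this stands, and it is why the point is minor. It does not make the unlabelled size and power in SAP 1.4 right for this trial.

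**429 is never printed.** It is a sum, and 379 appears in brackets under a heading about participants affected. But the rows are months of randomisation, the unbracketed counts add to the 50 called final, and the bracketed row is the group with no shortening. The reading is secure enough to raise, but the number should be confirmed against the randomisation system before it is written down.

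**Recruited might mean consented into the run-in.** The Synopsis speaks of enrolment, and some people are withdrawn before randomisation. This reading does not fit: SAP 1.3 has each subject stay for three years after recruitment, and the allowance in Protocol 6 d) covers treatment discontinuation and missing follow-up, both of which come after randomisation.

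**A reader might infer that the trial is underpowered.** The documents do not support that. They give no actual loss, and the 20-25% is a deliberate upper bound. Protocol 6 d) also says: "All those with a baseline and at least one follow up measurement will be included in analysis". Partial follow-up and the covariate adjustment planned in Protocol 15 may raise power above the table, while the shortened follow-up in Appendix 6 may lower it slightly.

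**Conclusion.** The concern holds as a minor reporting correction. SAP 1.4 presents a size of 500 when Appendix 6 implies 429, and at 429 its 90% power and its 20-25% loss allowance are not compatible on its own calculation: power is about 87% to 85%. Power stays at 90% or above if no more than about 11-12% lack usable follow-up.

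It would be wrong to conclude that the sample-size arithmetic was faulty, since it reproduces. It would also be wrong to conclude that the primary analysis or its interpretation has to change, since neither depends on the 500.

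The figures rest on a two-sided 5% test, equal arms, an unadjusted two-sample comparison, the plan's SD of 0.05 mm, and 429 being the randomised total.

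**What to change.** In SAP 1.4, keep the 500 and 200-per-arm calculation and label it as the original design basis. Then add:
- The number randomised: 429 by Protocol Appendix 6, to be confirmed against the randomisation system.
- Unadjusted two-sample power for 0.0167 mm (two-sided 5%, equal arms assumed) of 93%, 91%, 87% and 85% if 0%, 10%, 20% and 25% have no usable follow-up, with 90%-power differences of 0.0157, 0.0165, 0.0175 and 0.0181 mm.
- A caveat in both directions: partial follow-up and covariate adjustment may raise these figures, and the 1 to 8 months lost by each of the last 50 participants (175 participant-months, about 1% of the planned total) may lower them slightly.

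Put the same design-target label on the 500 in Protocol sections 1, 6 d) and 15. Only the passage in 6 d) is worded as an aim.

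The cost is a few sentences and labels. No analysis or decision rule changes, and no extra participants are needed.

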1.5. STUDY POPULATION

1.5.1. INCLUSION CRITERIA

Subjects with a confirmed diagnosis of type 1 diabetes (i.e. diagnosis below age of 40 years and insulin use within one year of diagnosis) for five years or more, aged 40 or over, with $7.0 \leq \text{HbA1c} < 10.0\%$ ($53 - 86 \text{ mmol/mol}$) and at risk of CVD [i.e. three or more of the following CVD risk factors: $\text{BMI} \geq 27 \text{ kg/m}^2$; current $\text{HbA1c} > 8.0\%$ (64 mmol/mol); known CVD / peripheral vascular disease; current smoker; $\text{eGFR} < 90 \text{ ml/min/1.73m}^2$; confirmed micro- (or macro-) albuminuria (according to local assays and reference ranges); hypertension ($\text{BP} \geq 140/90\text{mmHg}$, or established hypertensive treatment); dyslipidaemia; strong family history of CVD; and duration of diabetes > 20 years].

1.5.2. EXCLUSION CRITERIA

$\text{eGFR} < 45 \text{ ml/min/1.73m}^2$; women of childbearing age not on effective contraception; pregnancy and/or lactation; Acute Coronary Syndrome or Stroke/TIA within the last three months; NYHA stage 3 or 4 heart failure; uncontrolled angina; significant hypoglycaemia unawareness; impaired cognitive function / unable to give informed consent; previous carotid surgery or inability to capture adequate carotid images; gastroparesis; history of lactic acidosis; other contraindications to metformin (hepatic impairment, known sensitivity to metformin, acute illness – dehydration, severe infection, shock, acute cardiac failure, suspected tissue hypoxia; any coexistent life threatening condition including prior diagnosis of cancer within two years; history of alcohol problem or drug abuse; diabetes other than type 1 diabetes; and involvement in a clinical trial involving an investigational medicinal product within the last six months.

1.6. STATISTICAL ANALYSIS PLAN (SAP)

1.6.1. SAP OBJECTIVES

The objective of this SAP is to describe the statistical analyses to be carried out for the final analysis of the REMOVAL study.

1.6.2. GENERAL PRINCIPLES

All study data will be summarised as a whole and by treatment group at each study assessment point. Continuous variables will be summarised by the number of observations, number of missing values, mean, standard deviation (SD), median, quartiles and range. Categorical variables will be summarised by the number of observations, number of missing values and the number and percentage of individuals in each category.

Baseline data will be extracted from the Treatment Visit 1 electronic case report form (eCRF) page where possible; if values are missing, then data from the first screening visit (Run-in Visit 1) will be used.

The primary analysis, and all secondary analyses, will be carried out using all randomised individuals who provide sufficient data to conduct the particular analysis, regardless of their adherence to study protocol. For the primary outcome, a sensitivity analysis will be carried out using a Per-Protocol dataset, consisting of those individuals that completed the study according to protocol.

Graphical presentations will be specified and provided according to the results of the final analysis.

